8.4.5. Pre-existing Medical Conditions

A preexisting medical condition should be recorded as an AE only if the severity, frequency, or attribute of the condition worsens during the study (Except for the deterioration of the disease being studied). When recording such events, it is important to convey the concept that the pre-existing condition has changed by including applicable descriptors (e.g., "more frequent headaches").

8.4.6. Hospitalization, Prolonged Hospitalization or Surgery

Any AE that results in hospitalization or prolonged hospitalization should be documented and reported as an SAE, except as outlined below:

• Planned hospitalization or prolonged hospitalization required by the protocol (e.g.,

for investigational product administration or efficacy assessment)

Confidential

- Hospitalization due to existed medical conditions prior to the study and does not change. For example, elective surgery/treatment is scheduled before participating in the study.
- Hospitalization due to changes in living environment or social reasons rather than physical health (no medication or surgical intervention required), such as homeless, short of money, unattended, family environment, etc.

8.4.7. Pregnancy

In pregnant female subjects, study treatment must be discontinued immediately and notice the Investigator. The Investigator must report the pregnancies of a female subject or partner of a male subject occurring while the subject is on study treatment to the Sponsor within 24 hours. The Investigator should discuss with the subject the risk of continuing pregnancy and the possible effects on the fetus. Monitoring of the subject should continue until the end of pregnancy. Pregnancy occurring within 28 days (± 7 days) of the last investigational product administration should be reported to the Investigator.

Any manual and spontaneous abortion should be classified as an SAE. Any congenital anomaly/birth defect in a child born to a female subject or female partner of a male subject exposed to investigational product should be classified as an SAE and reported.

8.4.8. Overdose

Study treatment overdose is the accidental or intentional use of 3D185 in an amount higher than the protocol required dose.

When an overdose occurs, the Investigator must clarify whether there are any symptoms in the report. If drug overdose induced adverse reaction occurs, it should be reported as AE. If the adverse reaction meets the SAE requirement, it should be reported in accordance with the process and time limit of the SAE report. If it is only a drug overdose without any relevant clinical symptoms or laboratory abnormalities, the Investigator should report to the Sponsor within 24 hours after learning of the event, using the term "accident or intentional drug overdose without AEs" (Drug overdose itself should not be reported as AE or SAE).

8.4.9. Disease Progression

Disease progression will be considered, if a new lesion or existing lesion progress in the disease to be treated with the investigational product. Clinical symptoms and signs of confirmed progression will not be reported as AEs unless it is more severe than expected, or the Investigator believes that tumor progression is related to study administration or study procedures.

8.4.10. New Disease

If a new primary malignancy is present, it will be considered as SAE. If a disease is detected after treatment with the investigational product and is not the indication of the study, it will be defined as a new tumor.

8.5. Assessment of Adverse Events

8.5.1. Assessment of Severity

The Investigator will make an assessment of severity for each AE and SAE reported during the study according to the NCI CTCAE Version 4.03.

In addition, the severity of each AE and SAE should also be assigned to one of the following categories:

- Grade 1: Mild; asymptomatic or mild symptoms; clinical or diagnostic observations only; intervention not indicated.
- Grade 2: Moderate; minimal, local or noninvasive intervention indicated; limiting age-appropriate instrumental activities of Daily Living (refer to preparing meals, shopping for groceries or clothes, using the telephone, managing money, etc.).
- Grade 3: Severe; severe medically significant but not immediately life-threatening; hospitalization or prolongation of hospitalization indicated; disabling; limiting selfcare activities of Daily Living (refer to bathing, dressing and undressing, feeding self, using the toilet, taking medications, and not bedridden.).
- Grade 4: Severe; Life-threatening consequences; urgent intervention indicated.
- Grade 5: Severe; Death related to AE.

The severity and seriousness of AEs should be distinguished. The severity is used to describe intensity which may not an SAE. For example, a headache may be severe in intensity, but not an SAE unless it meets the criteria for SAE.

The NCI CTCAE version 4.03 doesn't include the classification of hyperphosphatemia. The grade of hyperphosphatemia in this study is defined as: Grade 1: > ULN ~ 7 mg/dL; Grade 2: > 7 mg/dL ~ 9 mg/dL; Grade 3: > 9 mg/dL).

8.5.2. Assessment of Causality

The Investigator is obligated to assess the relationship between the investigational product and the occurrence of each AE or SAE. The Investigator will use clinical judgment to determine the relationship. Alternative causes, such as the natural history of the underlying diseases, concomitant therapy, other risk factors, and the temporal relationship of the event to the investigational product will be considered and investigated. The Investigator will also consult the Investigator's brochure (IB) in the determination of his/her assessment.

There may be situations when an SAE has occurred, and the Investigator has minimal information to include in the initial report to the Sponsor. However, it is very important that the Investigator always makes an assessment of causality for every event prior to transmission of the SAE. The Investigator may change his/her opinion of causality in light of follow up information, updating the SAE report accordingly. The causality assessment is one of the criteria used when determining regulatory reporting requirements.

The Investigator will determine the relationship between an AE and the investigational product based on the following criteria:

- 1) Definitely: An event that follows a reasonable temporal sequence from administration of the investigational product; that follows a known or expected response pattern to the investigational product; that is improved by stopping or reducing the dosage of the investigational product; that is recurred by resuming the dosage of the investigational product.
- 2) Probably: An event that follows a reasonable temporal sequence from administration of the investigational product; that follows a known or expected response pattern to the investigational product; that may be caused by the subject's clinical state or by other interventions.
- 3) Probably unrelated: An event that doesn't follow a reasonable temporal sequence from administration of the investigational product; that doesn't follow a known or expected response pattern to the investigational product; that may be caused by the subject's clinical state or by other interventions.
- 4) Unrelated: An event that doesn't follow a reasonable temporal sequence from administration of the investigational product; that follow a known or expected response pattern to the non-investigational product; that may be caused by the subject's clinical

Confidential

state or by other interventions; that is improved or disappeared by stopping the dosage of the other treatment option; that is recurred by resuming the dosage of the other treatment option.

5) Uncertainty: An event that doesn't follow a reasonable temporal sequence from administration of the investigational product; that is similar to a known or expected response pattern to the investigational product; that may be caused by combining with other drugs.

When judging "Uncertainty", the Investigator should follow up, and make a clear causality

in the follow-up report.

The "definitely", "Probably" and "Uncertainty" AEs will be considered as investigational drug related AEs.

8.6. Adverse Events Follow-up

After the initial AE or SAE report, the Investigator is required to proactively follow each subject and provide further information to the Sponsor on the subject's condition.

All AEs and SAEs documented at a previous visit/contact and are designated as ongoing, will be reviewed at subsequent visits/contacts.

All AEs and SAEs will be followed until resolution, until the condition stabilizes, until the event is otherwise explained, or until the subject is lost to follow up. Once resolved, the appropriate AE or SAE will be updated.

The Investigator will ensure that follow up includes any supplemental investigations as may be indicated to elucidate the nature and/or causality of the AE or SAE. This may include additional laboratory tests or investigations, histopathological examinations, or consultation with other health care professionals.

The Sponsor may request that the Investigator perform or arrange for the conduct of supplemental measurements and/or evaluations to elucidate as fully as possible the nature and/or causality of the AE or SAE.

New or updated information will be recorded on the originally SAE report, with all changes signed and dated by the Investigator. The updated SAE report should be resent to the Sponsor as soon as possible.

After the safety follow-up visit, the Investigator needs to continue follow-up the AEs based on the criteria as below.

Investigational drug-related AEs will be followed up to meet one of the following criteria:

- Return to baseline;
- The severity reduced to level 2;
- Death;
- Start new anti-tumor treatments;
- The Investigator judges the AE is stable and will not improve further;
- No clinical or safety data is collected, or the final database is locked.

Investigational drug-unrelated serious or life-threatening AEs will be followed up to meet one of the following criteria:

- Return to baseline;
- Correlation is reassessed as unrelated;
- Death;
- Start new anti-tumor treatments;
- The Investigator judges the AE is stable and will not improve further;
- No clinical or safety data is collected, or the final database is locked.

Investigational drug-unrelated Grade 1-2 AEs will be followed up to 28 days after the last dose, which is the safety follow-up visit.

Investigational drug-related SAEs that occur after safety follow-up are also required to be reported, documented, and followed up.

The final outcome of each AE must be recorded to the eCRF.

8.7. Reporting Serious Adverse Events

8.7.1. Timeframes for Submitting Serious Adverse Events

The Investigator should report the initial SAE to the Sponsor with 24 hours of discovery. The frequency of follow-up visits will be determined based on the Investigator's opinion. The processing time for the follow-up SAE report should be the same as initial SAE report.

8.7.2. Completion and Transmission of the Serious Adverse Event Report

Once an Investigator becomes aware that an SAE has occurred in a subject, he/she must report the information to the Sponsor. If the Investigator does not have all information regarding an SAE, he/she will not wait to receive additional information before notifying the Sponsor of the event and completing the form. The form will be updated when additional information is received. The Investigator will always provide an assessment of causality at each time of the SAE report. The SAE report will always be completed as thoroughly as possible with all available details of the event, signed by the Investigator or designee.

A copy of the SAE report will be sent to a project contact who is responsible for receiving the SAE report by priority email. In rare cases, sending a fax is also acceptable.

A copy of the SAE form must be emailed within 24 hours to the attention of 3DMedDrug Safety and Pharmacovigilance at:

Sponsor fax and email: [name], [contact]

In addition to reporting all SAEs to the Sponsor, the Investigator must report the safety report to the local regulatory authority and other regulatory agencies. The Sponsor should also submit the safety report that occurred in this study to the regulatory authority in accordance with the requirements of the regulations.

The SUSAR report needs to be cross-submitted to NMPA and FDA, and the time limit should be in accordance with local regulations.

8.8. Post-study Adverse Events and Serious Adverse Events

A post-study AE/SAE is defined as any AE/SAE that occurs outside of the safety follow-up visit. Investigator is not obligated to actively seek AEs or SAEs in former subjects. However, if the Investigator learns of any SAE, including a death, at any time after a subject has been discharged from the study, and he/she considers the event reasonably related to the investigational product, the Investigator will promptly notify the Sponsor.

8.9. Precautions

To determine the reporting requirements for individual SAE, the Sponsor will evaluate the expectation of these events via the IB.

9. DATA ANALYSIS AND STATISTICAL

9.1. Sample Size Determination

The final sample size for the dose escalation study will depend on the number of dose levels evaluated and the occurrence of DLT for each dose cohort. The maximum sample size is expected to be 42 subjects.

9.2. General Considerations for Data Analysis

Data will be listed and summarized using SAS® Version 9.2 or higher (SAS Institute, Inc., Cary, North Carolina) according to Sponsor agreed reporting standards, where applicable. Complete details will be documented in the SAP.

The following statistical analysis is performed based on the nature of the parameters:

- ♦ Continuous variables: number of non-missing observations, mean, standard deviation, median, minimum, and maximum.
- ♦ Categorical variables: frequencies and percentages.
- Time-to-event variables: number of non-missing observations (N), median, minimum, and maximum. Kaplan-Meier event rates may also be provided if applicable for specific time-to-event variables.

Further description of the statistical methods and analyses will be provided in the SAP.

9.2.1. Analysis Population

Full Analysis Set (FAS)

The FAS will include all subjects who received 3D185 treatment in this study. The FAS will be the primary population for evaluating all efficacy, safety and subject characteristics.

DLT Analysis Set (DLT set)

The DLT set will include all subjects who received at least \geq 75% of the planned doses of treatment and completed the safety assessment during DLT evaluation period. The frequency and severity of DLT will be analyzed.

PK Analysis Set (PKS)

The PK set will include subjects who have received at least one dose and have at least once evaluable PK sample collection after administration.

PD Analysis Set (PD set)

The PD set will include subjects who have received at least one dose and have at least once serum phosphate level measurement (serum biochemistry) after administration.

9.3. Efficacy Analyses

The Investigator will perform the tumor assessment according to RECIST Version 1.1 at screening and every 8 weeks after the first dose in Cycle 1. The best overall response will be classified into progressive disease, SD, CR and PR. A summary by category and a listing will be provided.

ORR is defined as the proportion of subjects who achieve a BOR of CR or PR in the full analysis set. Estimate of ORR and its 95% exact confidence interval (CI) (Clopper-Pearson) will be provided.

The DCR is defined as the proportion of subjects whose BOR achieve a disease control (CR, PR, or SD) in the full analysis set. Estimate of DCR and its 95% exact CI (Clopper-Pearson) will also be provided.

9.4. Safety Analysis

Safety data include AEs, physical examinations, vital signs, laboratory evaluations, ECG, ophthalmological examination, etc. All AEs will be coded using the latest version of MedDRA. The severity of AE will be graded according to NCI CTC AE V4.03 (Grade 1

to 5). All treatment emergent AEs frequency will be summarized by system organ class (SOC) and preferred term (PT), and also be further summarized based on the worst grade per NCI CTCAE v4.03 and relationship to investigational product. The number and the percentage of subjects reporting DLT events in each dose cohort during the dose escalation phase will be summarized. The relationship between exposure level and safety of 3D185 in all subjects (E-R model) will be analyzed.

9.5. Pharmacokinetics Analysis

For the PK parameters, in addition to the above general analysis, the coefficient of variation, geometric mean, and geometric coefficient of variation will be used for statistical description.

The concentration-time curve and the average concentration-time curve of each subject will be plotted based on the plasma concentration-time data measured in the trial. The PK parameters will be calculated using standard non-compartment models and WinNonlin[®] Professional 6.4 or higher version (Certara, Princeton, NJ, USA) or SAS[®] 9.3 or higher version (SAS Institute, Inc., Cary, North Carolina) to fully reflect the drug absorption, distribution and elimination characteristics in the human body. The interim PK parameters will be calculated using the planned blood collection time, and the final PK parameters will be calculated using the actual blood collection time.

- Power Model will be used to assess the dose proportionality. $log(y) = \beta 0 + \beta 1*log(dose)$, where y is the PK parameter (AUC_{0-tau}, C_{max}), $\beta 0$ is the intercept, and $\beta 1$ is the slope. The 90% CI for slope $\beta 1$ will be estimated using a mixed-effects model, with the treatment group as a fixed effect, and then using CIs for linear pharmacokinetic evaluation.
- The potential relationship between dose level, PK variables, clinical safety and the preliminary clinical efficacy will be explored.
- The detailed analysis of the specific content in SAP.

10.ETHICS

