4. STUDY DESIGN AND PLAN

4.1. Overall Plan

This is an open-label, global multicenter, dose-escalation phase 1 study of 3D185 monotherapy in subjects with advanced solid tumors.

The starting dose in this dose-escalation study is 25 mg, and the preset 7 dose-escalation cohorts are 25 mg, 50 mg, 100 mg, 150 mg, 200 mg, 250 mg, and 300 mg, respectively. This study adopts a combination of accelerated titration and i3+3^[1] for dose escalation. All subjects in each cohort will receive a single oral dose of 3D185, followed by a 7-day washout period (i.e. single-dose PK study period). Then, subjects will receive consecutive daily doses (QD, 28 days/cycle) until disease progression, death, unacceptable toxicity, or withdraw of informed consent, whichever comes first. The DLT evaluation period includes the single-dose PK study period and the first treatment cycle (within 35 days after the first dose). The enrolled subjects will be sequentially assigned to the planned dose cohorts according to the protocol, and receive 3D185 treatment to observe the occurrence of DLT:

Accelerated titration dose-escalation phase: One subject is to be enrolled sequentially to 25 mg and 50 mg cohorts, respectively. If no Grade ≥ 2 drug-related AE occurs during DLT evaluation period, the study will escalate to the next dose level. Otherwise, 2 additional subjects will be enrolled, and the subsequent study will convert to i3+3 dose-escalation design from this dose cohort.

In the accelerated titration phase, a subject may be replaced if he/she 1) does not reach to 75% of the total planned dose; 2) discontinued investigational product due to non-DLT reasons during the DLT evaluation period.

i3+3 dose-escalation phase: Starting at 100 mg cohort, 3 subjects are to be enrolled initially at each subsequent dose cohorts in accordance to i3+3 dose-escalation design. Each dose cohort should recruit at least one subject from each country after sites in both countries are activated. If a cohort requires ≥ 6 subjects, it must enroll at least 1 subject from each country and efforts will be made to ensure number of subjects enrolled from each country is similar.

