After 3 subjects in each cohort completed DLT evaluation, the safety monitoring committee (SMC) will review all available safety and PK/PD data from all treated subjects (DLT evaluable and non-DLT evaluable subjects), taking into consideration the dose-assignment recommendation based on i3+3 decision rule (Figure 1; Section 4.2), to make the recommendation on the conduct of the study including the dose level for subsequent subjects. In addition, the SMC will review and evaluate all available safety data if one of the following criteria is met:

- More than 30% of all subjects who received 3D185 experienced serious adverse events (exclude unrelated events assessed by investigator);
- Any investigational product toxicity related death is reported.

Enrollment will be paused while SMC is reviewing the data until a formal decision is made by SMC. The recommendations made by SMC include the following:

- Recommend to start enrollment to the next higher dose level per protocol;
- Recommend to enroll more subjects at a given dose level;
- Recommend whether a lower dose or a different schedule should be evaluated;
- Recommend whether the study should be terminated;
- Recommend to modify the study design

Details of the safety monitoring process will be specified in a dedicated SMC charter.

If a Grade ≥ 2 drug-related AE occurs during the accelerated titration dose-escalation phase, the i3+3 dose-escalation phase will be initiated earlier. If the i3+3 dose-escalation phase starts from 100 mg, the maximum sample size in this phase will be 30 subjects; and, if i3+3 design starts at the dose of 50 mg or 25 mg, the maximum sample size will be 36 or 42, respectively.

If a subject terminates treatment due to non-DLT reasons during the first treatment cycle, there is no need to replace the subject. When the study has increased to a dose level (d) that is beyond the MTD, and according to the i3+3 decision table (Figure 1), the dose-assignment recommendations in cohorts of d and d-1 are dose de-escalation (D) and escalation (E), respectively, a new cohort may be added between the d and d-1 dose cohort after SMC review and evaluation on the available clinical data of PK/PD, safety, and efficacy, the new cohort can be an intermediate dose cohort (25 mg increment/decrement) or an intermittent schedule (such as 3 weeks on, 1 week off; 5 days on, 2 days off, etc.). The sample size will be increased by 6 subjects accordingly.

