At the end of the study, the MTD will be inferred based on the DLT data and all safety data observed at all dose levels. The specific MTD estimation method is shown in Section 4.2. The RPTD will be established by taking into consideration of the PK and/or PD profiles and safety data from the dose escalation phase.

The DLT evaluable subject is defined as the subject who received at least 75% of the planned doses of treatment and completed the safety assessment during DLT evaluation period.

During the DLT evaluation period, Subject can withhold 3D185 due to drug-related AEs. If the withholding time is more than 7 days, the AE will be considered as DLT. The subject's dose of 3D185 will not be reduced unless DLT occurs.

4.2. i3+3 Design

Similar to the 3+3 design^[18], the i3+3 is rule-based design, and it is also an interval-based design similar to mTPI^[19]. The specific algorithm of i3+3 design is shown in Appendix 7. Compared to the 3+3 design, the i3+3 design offers greater flexibility (e.g., flexible handling of subject, shedding), higher MTD selection probabilities, and better safety (see Appendix 8 for the comparison results of the simulation trials for 3+3 and i3+3). The target toxicity probability of the MTD in this study is set to pT = 25%, and the equivalence interval (EI) is (16%, 30%). This means

that the MTD should have a toxicity probability near 25% but not below 16% or above 30%. The decision table for the i3+3 design of this study is shown in Figure 1.

[figure not shown]

Figure 1 i3+3 Dose Escalation Decision Table

Note:

This is a decision table for the 3D185 dose-finding study. The target toxicity probability (pT) is 25% and the equivalence interval (EI) is (16%, 30%) for 42 subjects. Each column represents (n) number of DLT evaluable subjects treated at the current dose and each row represents (x) number of subjects with DLTs at the dose level. Each cell in the table provides the dose-assignment recommendation based on the readouts from the corresponding row (x) and column (n). The letters in the decision table represent different dose-assignment recommendations.

The i3+3 dose-escalation phase is expected to enroll 30-42 subjects (maximum sample size will be adjusted according to the first dose entering the i3+3 phase. For details, see Section 4.1). Every 3 subjects as a cohort will be sequentially enrolled.

The specific operation process of i3+3 design is as follows:

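### The dose-proportionality paragraph contradicts itself: with treatment group as a fixed effect, the power-model slope is not uniquely estimable

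*Protocol*

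**What the plan says.** Protocol section 9.5 (Pharmacokinetics Analysis) states "Power Model will be used to assess the dose proportionality". It writes the model as log(y) = β0 + β1·log(dose), where y is AUC0-tau or Cmax, β0 the intercept and β1 the slope. The equation has no group term and no random effect. The same bullet then says that the 90% CI for β1 "will be estimated using a mixed-effects model, with the treatment group as a fixed effect", and that linear pharmacokinetics will be judged from the CIs. No random effect is named, although the model is called mixed. Further PK detail is left to the SAP.

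Section 4.1 (Overall Plan) shows what a treatment group can be. The design is described as follows: "This is an open-label, global multicenter, dose-escalation phase 1 study of 3D185 monotherapy in subjects with advanced solid tumors". There is no comparator, and "the preset 7 dose-escalation cohorts are 25 mg, 50 mg, 100 mg, 150 mg, 200 mg, 250 mg, and 300 mg, respectively". Under the same section's rules for the DLT evaluation period, which contains all the PK sampling, "The subject's dose of 3D185 will not be reduced unless DLT occurs".

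**The concern.** The equation and the estimation sentence describe different models. If treatment group is the dose cohort, every subject in a group has the same planned log(dose). A categorical group term then absorbs all the variation in log(dose) and leaves nothing from which to estimate the slope. If group is instead fitted in place of log(dose), the model has no slope.

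At stake is the only method that the protocol names for judging linear pharmacokinetics. An analyst who follows the sentence as written gets either no slope or one whose value and CI depend on which column the software drops. An analyst who fits the equation alone departs from the sentence. Neither can say that the protocol was followed.

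**Working it through.** The protocol gives no figure for this analysis (no SD, no proportionality limits, no precision target), so there is nothing to reproduce. The check is whether β1 can be estimated, and what a forced fit would cost.

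**Inputs.** Doses are 25, 50, 100, 150, 200, 250 and 300 mg (section 4.1). Cohort sizes are assumptions built on sections 4.1 and 4.2: one subject each at 25 and 50 mg, then either three per i3+3 cohort (17 subjects) or six (2 + 30 = 32, since 30 is the maximum when i3+3 starts at 100 mg).

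**Step 1: estimability.**
- Equation alone (intercept, log dose): 2 columns, rank 2. β1 is estimable.
- Intercept, log dose and six cohort indicators: 8 columns, rank 7. After regressing log(dose) on group, the residual sum of squares is zero to machine precision. β1 is not estimable. The same holds with six subjects at all seven doses.
- Two records per subject (single dose and C1D28) plus a period effect: 9 columns, rank 8. Still not estimable.
- Section 4.1 allows an added cohort: "the new cohort can be an intermediate dose cohort (25 mg increment/decrement) or an intermittent schedule". Each added group still has one dose. An intermittent-schedule group at an existing dose (200 mg was tried) gives 9 columns, rank 8. Still not estimable.
- Group in place of log(dose): the model contains no β1.

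**Step 2: what a forced fit would give.** Suppose the software keeps log(dose) and drops one further indicator. Five cohorts are then fitted exactly by their own indicators, and the slope comes from the two cohorts i and j left without one. In units of the residual SD:

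- plain power model: SE = 1/√Sxx, with Sxx = Σ n_k (x_k − x̄)² and x = ln(dose);
- two cohorts: SE = √(1/n_i + 1/n_j) / ln(dose_j/dose_i).

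With 1,1,3,3,3,3,3 subjects:
- Sxx = 7.375, so the plain SE is 1/√7.375 = 0.368.
- 25 vs 300 mg: √(1 + 1/3)/ln(12) = 1.155/2.485 = 0.465; ratio 0.465/0.368 = 1.26.
- 250 vs 300 mg: √(1/3 + 1/3)/ln(1.2) = 0.816/0.182 = 4.48; ratio 4.48/0.368 = 12.2.
- Over all 21 pairs, the ratio runs from 1.26 to 12.2, median about 2.9.

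With 1,1,6,6,6,6,6 subjects:
- Sxx = 9.938, so the plain SE is 0.317.
- 25 vs 300 mg: √(1 + 1/6)/2.485 = 0.435; ratio 1.37.
- 250 vs 300 mg: √(1/6 + 1/6)/0.182 = 3.17; ratio 10.0.
- Over all 21 pairs, the ratio runs from 1.37 to 10.0, median 2.6.

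The point estimate moves too. In one simulated data set (true slope 1, assumed SD 0.5 on the log scale, 32 subjects), the two-cohort slopes ran from 0.46 to 2.56, against 0.87 from the plain power model.

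**The case against.** The strongest reply is that the clause is loose wording. The equation is written out in full, has no group term and is estimable. The next sentence does not say that group is added to it. Treatment group is not defined in section 9.5, so equating it with the dose cohort is an inference, though the only sensible one here. The author may have meant that dose, entered as log(dose), is the fixed part of the model. This stands as a possible intent, but the text does not say so, and both literal readings fail. A second reply is that detail is deferred to the SAP. That may mean the fault is corrected there, but it does not correct a sentence in which the protocol names the term.

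A reader might infer more than the documents support:

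- **That precision falls about 12-fold.** That is the worst of the 21 pairs with three subjects per i3+3 cohort. Which pair results depends on column order and level sorting, which the protocol does not state. If group enters first, the slope column itself may be dropped and there is no SE at all.
- **That the recommended dose is put at risk.** Section 4.1 bases it on PK and/or PD profiles and safety data generally. No passage makes the CI for β1 an input, and section 9.5 ties no decision limit to it.
- **That the MTD is affected.** Section 4.2 selects it by isotonic regression on DLT data together with all safety data.

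A dose reduction after a DLT could create some within-cohort variation if actual dose were analysed. β1 would then rest on those few subjects alone, so this does not rescue the model.

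**Conclusion.** The point holds as an internal contradiction in section 9.5. With a dose-cohort fixed effect beside log(dose), β1 is not uniquely estimable (8 columns, rank 7); with that effect in place of log(dose), β1 does not exist. A forced fit would have an SE of about 1.3 to 12 times that of the plain model with three subjects per i3+3 cohort, or 1.4 to 10 times with six.

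The conclusion rests on treatment group meaning the dose cohort and on planned dose being analysed. The SE ratios also rest on the assumed cohort sizes and a common residual SD. The reach is limited to the secondary dose-proportionality analysis. The documents do not show that the analysis will fail in practice, because the intent may have been the plain power model.

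**What to change.** In section 9.5, delete the clause that makes treatment group a fixed effect, and state that log(dose), as a continuous covariate, is the only dose term in the model for each PK parameter. Use ordinary linear regression where there is one record per subject. Keep a mixed-effects model, with subject named as the random effect, only if single-dose and C1D28 records are pooled.

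β1 is then estimable. As an illustration, with one record per subject and an assumed between-subject SD of log(y) of 0.3, 0.5 or 0.7 (the protocol gives none), the 90% CI half-width is 0.19, 0.32 or 0.45 with 17 subjects, and 0.16, 0.27 or 0.38 with 32.

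The cost is a change of wording in one bullet, carried into the SAP. Data collection, sample size and the dose-escalation rules are unchanged.
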